### **9.3 Study File and Archiving**

The Investigator(s) shall maintain a Study File for the study purpose. This file contains all relevant documents necessary for the conduct of the study. This file must be safely archived after termination of the study in accordance with the local relevant regulations.

## 11 APPENDIX Schedule of Assessments

Procedures	Screening	Treatment Period (bintralusp alfa until PD; unacceptable toxicity; death or withdrawal; maximum of 2 years)										Disease Progression
		Cycle 1 m Cycle = 14 Days ± 7 Days		Cycle 2	Cycle 3	Cycle 4	Cycle 5	Cycle 6	Cycle 7	Cycle 8	Cycle 9 and thereafter	
		Day -28 - 0	Day 1	Day 1	Day 1	Day 1	Day 1	Day 1	Day 1	Day 1	Day 1	
Tests and Observations												
Informed Consent d	x											
Medical History	x											
Physical Examination (including skin examination) e	x	x	x	x	x	x	x	x	x	x	x a	x
Vital Signs	x	x	x	x	x	x	x	x	x	x	x a	x
ECOG Performance Status	x	x	x	x	x	x	x	x	x	x	x a	x
ECG	x	x				x					x b	x
Adverse Event Evaluation	x	x	x	x	x	x	x	x	x	x	x a	x
Concomitant Medication Review	x	x	x	x	x	x	x	x	x	x	x a	x
Laboratory Tests												
CBC f	x	x	x	x	x	x	x	x	x	x	x a	x
Coagulation Test h	x	x	x			x	x	x	x	x	x b	x
Comprehensive Serum Chemistry Panel g	x	x	x	x	x	x	x	x	x	x	x a	x
Exploratory blood-based biomarkers i	x	x i	x	x i	x	x i	x	x i	x i	x	x i	x
Urinalysis	x	x	x	x	x	x	x	x	x	x	x a	x
Pregnancy Test j	x						x				x c	x
Thyroid Function Test		x		x		x		x		x	x c	x
Cortisol 9AM		x		x		x		x		x	x c	x
Disease Assessment												
CT Scan (Head, Neck, Chest, Abdomen, Pelvis) k	x	x				x				x k	x	
MRI Scan (Brain)												
Survival follow-up	x		x				x					x
Quality of life assessment l	x		x				x				x	x

- a. Assessments/procedures are to be performed on Day 1 every cycle and prior to treatment unless otherwise specified.
- b. Assessments and procedures are to be performed on Day 1 every 4 cycles and prior to treatment unless otherwise specified.
- c. Assessments and procedures are to be performed on Day 1 every 2 cycles and prior to treatment unless otherwise specified.
- d. Informed Consent must be obtained  $\leq$  28 days prior to the initiation of trial treatment.
- e. Physical examinations will include measurements of weight and vital signs (resting heart rate, blood pressure, respiratory rate, temperature).
- f. Hematology parameters include the following laboratory tests: complete blood count with 3-part differential (i.e. total neutrophil count including bands, lymphocytes, and monocytes), hemoglobin, hematocrit and platelets.
- g. Blood chemistry must include glucose, BUN, creatinine (eGFR), sodium, potassium, magnesium, chloride, calcium, CO2, alkaline phosphate, AST (SGOT), total bilirubin, total protein, albumin, phosphorus, uric acid.
- h. Coagulation test include PT, PTT and INR.
- i. Plasma EBV DNA will be determined before treatment and every 2 weeks until disease progression; plasma TGF $\beta$ 1 measurement will be performed every 8 weeks until disease progression; PD-L1 concentration in the exosome will be measured every 2 weeks until disease progression.
- j. Pregnancy test will be performed within 1 week prior to treatment, if a cycle is missed during treatment or pregnancy and at the end of treatment visit only for women of childbearing potential.
- k. Patients will have CT scan at Screening/Baseline ( $\leq$  28 days prior to initiation of trial treatment), every 8 weeks for the first 12 months, and every 12 weeks thereafter. Patients will also have CT scan whenever disease progression is suspected. For patients who discontinue treatment without radiographic progression per RECIST 1.1 (e.g. in patients who discontinue treatment for clinical progression or adverse reactions), disease assessment should continue as stated in schedule until radiographic disease progression or alternate therapy is given.
- l. Quality of life (QoL) will be assessed by patient-reported EORTC QLQ-C30 and H&N-35 questionnaires every 12 weeks in the first year.
- m. If screening assessments were completed within 28 days, they do not need to be repeated on Day 1 of Cycle 1 if patient's condition has not changed.

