### 5.3 Handling of the Dosage Form

For applications in clinical studies, the freeze-dried drug product must be reconstituted with 4.5 mL of water for injection and further diluted with 0.9% saline solution (sodium chloride injection)

supplied in an infusion bag. The liquid formulation is diluted directly with 0.9% saline solution. The estimated volumes of delivery are anticipated to be either 250 mL or 500 mL, which are clinically acceptable. Detailed information on infusion bags and medical devices to be used for the preparation of the dilutions and subsequent administration, and assigned dose levels and concrete volumes to be replaced to prepare the target doses are described in the Pharmacy Manual.

Bintrafusp alfa 1200mg will be administered intravenously on Day 1 of each 2-week study cycle. Bintrafusp alfa may be administered up to 3 days before or after the scheduled day of administration of each cycle due to administrative reasons.

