### **5.6.10 Embryo-Fetal Toxicities**

Embryofetal toxicities are known risk of the PD 1/PD L1 targeting class and are considered important potential risks for bintrafusp alfa. Animal models link the PD 1/PD L1 signaling pathway with maintenance of pregnancy through induction of maternal immune tolerance to fetal tissue. Embryofetal toxicity is an important potential risk of bintrafusp alfa. An appropriate contraception warning is provided as part of the inclusion criteria. Pregnant and breastfeeding women are not allowed in the bintrafusp alfa study, and adequate contraceptive measures are recommended during the study to minimize or eliminate the potential risk to the developing fetus

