## **6 FOLLOW UP AND OUTCOME EVALUATION**

### **6.1 Follow-Up Schedule**

All participants will be followed every 2 weeks during the intervention. At each visit, patient's performance status and toxicity of treatment will be monitored, and blood test will be checked for complete blood count, liver function, and renal function. Thyroid function test and early morning cortisol (9am) will be performed at least every 4 weeks while on bintrafusp alfa therapy. For female patients in reproductive age, urine or serum pregnancy test needs to be performed at least every month while the subject is on bintrafusp alfa therapy. All adverse events and laboratory abnormalities will be graded per the National Cancer Institute Common Terminology Criteria for Adverse Events, version 4.0.

For blood-borne immune markers and exploratory biomarkers, plasma EBV DNA will be determined before treatment and every 2 weeks until disease progression; plasma TGF $\beta$ 1 measurement will be performed every 8 weeks until disease progression; exo-PD-L1 concentration will be measured every 2 weeks until disease progression.

Tumor imaging by CT head, neck, chest, abdomen, and pelvis will be done at baseline, every 8 weeks for the first 12 months, then every 12 weeks thereafter. Response will be assessed per RECIST version 1.1. Treatment decisions will be based on Investigator(s) review.

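### Pregnancy testing on treatment is set three ways, and neither the schedule grid in Cycles 1–8 nor its footnote j delivers the monthly test that Section 6.1 requires

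*Protocol*

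**What the plan says.** Three places in the Protocol govern pregnancy testing during treatment.

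- **Section 6.1, Follow-Up Schedule.** For female patients of reproductive age, a "urine or serum pregnancy test needs to be performed at least every month while the subject is on bintrafusp alfa therapy".
- **Section 11, Schedule of Assessments, footnote j** (attached to the Pregnancy Test row). It begins "Pregnancy test will be performed within 1 week prior to treatment, if a cycle is missed during treatment"; the full trigger clause reads "if a cycle is missed during treatment or pregnancy and at the end of treatment visit only for women of childbearing potential".
- **Section 11, the grid itself.** The Pregnancy Test row is marked at screening, once somewhere in Cycles 1–8, at Cycle 9 and thereafter under footnote c, and at disease progression. Footnote c says: "Assessments and procedures are to be performed on Day 1 every 2 cycles and prior to treatment unless otherwise specified".

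Two other statements bear on the point. Section 6.1 sets a comparable rule for another safety test: "Thyroid function test and early morning cortisol (9am) will be performed at least every 4 weeks while on bintrafusp alfa therapy". Section 5.6.10 gives the reason for testing: "Embryofetal toxicity is an important potential risk of bintrafusp alfa".

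**The concern.** The three rules cannot all be followed as the complete schedule. Section 6.1 sets a calendar minimum for the whole of treatment. Footnote j names occasions (before treatment, a missed cycle, end of treatment) and no routine interval. The grid sets a third pattern: sparse in Cycles 1–8, four-weekly afterwards.

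Footnote j is also unclear in itself. Elsewhere in the appendix a cycle is a dosing cycle, but here it could equally be a menstrual cycle. The phrase about a cycle being missed during treatment or pregnancy cannot be applied as written.

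Staff who book tests from the grid and its footnotes would depart from Section 6.1 and test too rarely during the first 16 weeks, for a risk the Protocol itself lists as important. These women would be under-monitored, not unmonitored. Effective contraception and a negative baseline test (Section 3.1) and the instruction to report a pregnancy at once (Section 6.6.4) all remain. But the Protocol asks for monthly testing in addition to those safeguards.

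**Working it through.** No sample-size or error-rate figure is involved. The check is a count of days and tests.

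**Inputs**

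- Cycle length is 14 days. Section 5.3: "Bintrafusp alfa 1200mg will be administered intravenously on Day 1 of each 2-week study cycle".
- Required interval *m* is at most one month, taken as 28, 30 or 31 days (Section 6.1).
- Tests marked strictly between Cycle 1 Day 1 and Cycle 9 Day 1: one in the grid, none routinely under footnote j.
- From Cycle 9: every two cycles (footnote c).

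**Length of the span.** Cycle *k* Day 1 falls 14(*k* − 1) days after Cycle 1 Day 1. Cycle 9 Day 1 is therefore day 14 × 8 = 112, or 16 weeks.

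**Tests needed inside the span.** The number is ceil(112/*m*) − 1.

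- *m* = 28: 112/28 = 4, so 3 tests
- *m* = 30: 112/30 = 3.73, rounded up to 4, so 3 tests
- *m* = 31: 112/31 = 3.61, rounded up to 4, so 3 tests

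Day 1 of Cycles 3, 5 and 7 would do it. The grid provides 1 and footnote j guarantees 0.

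**Longest gap with a single mark at Cycle *k*.** This is max{14(*k* − 1), 112 − 14(*k* − 1)}.

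| Mark at Cycle | Gap from Cycle 1 (days) | Gap to Cycle 9 (days) | Longest (days) |
|---|---|---|---|
| 3 | 28 | 84 | 84 |
| 4 | 42 | 70 | 70 |
| 5 | 56 | 56 | 56 |
| 6 | 70 | 42 | 70 |
| 7 | 84 | 28 | 84 |

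In the copy of the grid I worked from, the body has one column more than the header names, so the mark belongs to Cycle 5 or Cycle 6. The result does not depend on which: the smallest possible longest gap over Cycles 1–8 is 56 days. Counting from Cycle 1 Day 1 also favours the grid, because footnote j lets the baseline test be up to a week earlier.

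**Effect of visit windows.** Section 5.3 lets each dose move 3 days either way. In the most favourable case the span shortens to 112 − 6 = 106 days, and the longer of the two gaps is still at least 106/2 = 53 days.

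**From Cycle 9.** The interval is 2 × 14 = 28 days, which nominally meets Section 6.1.

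**Internal comparison.** The thyroid function and cortisol rows in the same grid carry alternating marks through Cycles 1–8, as their four-weekly rule in Section 6.1 requires. The Pregnancy Test row does not.

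**Reach.** The two anti-PD-1 cohorts described in Section 1 were 77.8% male. If this trial is similar (an assumption), 38 × (1 − 0.778) = 8.4, so about 8 women, with fewer of childbearing potential.

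**The case against.** The strongest reply is that the texts can be read together. Section 6.1 states the only routine interval and sets a minimum. Footnote j lists occasions and nothing in it cancels the monthly test, so it could simply add to Section 6.1. On that reading the dispute shrinks to the number of marks in one row of a table that is hard to read. That reading of footnote j is possible, but it leaves the grid two tests short in Cycles 1–8, and the Protocol has no clause saying which text prevails. Marks lost in reproduction are an unlikely explanation, because the neighbouring thyroid and cortisol rows keep theirs.

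Footnote j might also be read as asking for a test before every dose. That would satisfy Section 6.1. But it would make the missed-cycle trigger redundant and contradict the grid more sharply.

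A fair point concerns the windows. The grid header allows 14 ± 7 days per cycle, Section 5.3 allows 3 days either way, and doses may be omitted or held. Two nominal cycles can then run to 28 + 6 = 34 days under Section 5.3, or 2 × 21 = 42 days under the header. The 28-, 56- and 70-day figures are therefore nominal, and marks tied to cycles do not by themselves secure a calendar rule. This stands, and it is why the footnote should state the interval in weeks.

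It also stands that other safeguards exist, that few patients are affected, and that no endpoint or decision rule is touched.

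**Conclusion.** The concern holds. Section 6.1, footnote j and the grid give different rules for pregnancy testing on treatment, and in Cycles 1–8 neither part of the appendix secures the monthly test: one test (grid) or none routinely (footnote j) against the three needed in 112 days. The longest nominal gap is at least 56 days, or 70 if the mark sits at Cycle 6. From Cycle 9 the grid agrees with Section 6.1 on nominal timing.

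The monthly rule is sound; the fault is that the appendix does not carry it out. The conclusion assumes 14-day cycles and that the row truly has a single mark in Cycles 1–8, which is easily confirmed on the source table. Footnote j's failure to state the monthly rule is in running text and does not depend on the table. The consequence is limited to safety monitoring in a small subgroup. It deserves correction because the risk is one the Protocol names as important and the correction is simple.

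**What to change.** Keep Section 6.1 as the governing rule and bring the appendix into line.

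1. Mark the Pregnancy Test row every two cycles from Cycle 1, as is done for thyroid function and cortisol.
2. Replace footnote j with wording such as: *For women of childbearing potential: within 1 week before the first dose, at least every 4 weeks on treatment, whenever a menstrual period is missed or pregnancy is suspected, and at the end-of-treatment visit.*

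Stating the interval in weeks keeps the rule in force when cycles are delayed or doses are held, and naming the menstrual period removes the ambiguity over the word cycle. The cost is a change to one table row and one footnote. No test is added beyond those Section 6.1 already requires.

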## 6.2 Outcome Measures

Primary outcome:

- Objective response rate (ORR): The percentage of patients with radiologically complete or partial response as determined by the Investigator according to RECIST version 1.1.

Secondary outcomes:

- Progression-free Survival (PFS): PFS is measured from the date of informed consent to radiographically documented progression according to RECIST 1.1 or death from any cause (whichever occurs first). Participants alive and without disease progression or lost to follow-up will be censored at the date of their last radiographic assessment
- Time to progression (TTP): TTP is measured from the date of informed consent to radiographically documented progression according to RECIST 1.1. Participants death and without disease progression, alive without disease progression, or lost to follow-up will be censored at the date of their last radiographic assessment
- Overall survival (OS): OS is measured from date of informed consent to the date of death from any cause. Participants alive or lost to follow-up will be censored at the date of their last radiographic assessment

Survival rate at 12 months and 24 months: The percentage of study population who are still alive for 12 months and 24 months from the date of study enrollment. Participants alive or lost to follow-up will be censored at the date of their last radiographic assessment

Duration of response (DOR): DOR is the time from documentation of tumor response to radiographically documented disease progression

- ORR, TTP, and PFS of the same definitions as above are measured against immune-related RECIST (irRECIST) criteria as one of the secondary endpoints.
- Safety outcome measures: Incidence, nature, and severity of adverse events graded according to the National Cancer Institute Common Terminology Criteria for Adverse Events (NCI-CTCAE v.4)
- Pre-treatment, serial post-treatment plasma EBV-DNA levels, and dynamics of

EBV DNA levels will be measured

- Disease control rate (DCR): The percentage of patients with a CR, PR, or SD  $\geq$  6 months per RECIST 1.1
- Time to response (TTR): TTR is measured from the date of informed consent to first radiographically documented tumor response per RECIST 1.1
- Quality of life (QoL): as assessed by the European Organization for Research and Treatment of Cancer Core Quality of Life Questionnaire (EORTC-QLQ-C30) and the head and neck cancer-specific H&N-35 questionnaires

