## 7 STATISTICS

### 7.1 Statistical Analysis

Objective response rate (ORR) will be expressed based on exact binomial distribution. Survival outcomes, including TTP, PFS, OS, and survival rate their corresponding 95% confidence interval, will be estimated using Kaplan-Meier method. The Fisher exact test will be used to correlate the binary clinical and biomarker data. The cut-off values of baseline and changes in the exo-PD-L1 and TGF- $\beta$ 1 levels will be calculated by the Receiver Operating Characteristic (ROC) curve analyses.

All of the reported P values will be 2-tailed, and P<0.05 will be considered statistically significant. No multiplicity will be considered. The analyses will be performed using statistical software packages SPSS and R.

**Procedures for Handling Missing, Unused, and Spurious Data:** All available data will be included in the data listings and tabulations. Where appropriate, imputations of values for missing data for primary and secondary efficacy analyses will be performed as specified in the Statistical Analysis Plan. All data recorded on the CRF will be included in the data listings that will accompany the clinical study report.

If, after the study has begun, but prior to the conduct of any analysis, changes made to primary and / or key secondary endpoints, or the statistical methods related to those hypotheses, then the protocol will be amended. Changes to exploratory analyses made after the protocol finalized will be documented and referenced in the final report. Post hoc exploratory analyses will also be identified in the final report.

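### Footnote m lets a screening sample up to 28 days old stand in for the Cycle 1 Day 1 marker sample, so baseline and change in EBV DNA, TGF-β1 and exosomal PD-L1 may not share a common starting point

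*Protocol*

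**What the plan says.** The Schedule of Assessments has a row headed "Exploratory blood-based biomarkers", marked at screening (Day -28 to 0) and at Cycle 1 Day 1. Footnote m is attached to the Cycle 1 column header and reads "If screening assessments were completed within 28 days, they do not need to be repeated on Day 1 of Cycle 1", with the condition "if patient's condition has not changed". It names no row as exempt.

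Footnote i governs the biomarker row. For EBV DNA it states "Plasma EBV DNA will be determined before treatment and every 2 weeks until disease progression". For exosomal PD-L1 it states "PD-L1 concentration in the exosome will be measured every 2 weeks until disease progression", and for TGF-β1 "measurement will be performed every 8 weeks until disease progression". Section 6.1 repeats these rules. Section 6.5 refers to pre-treatment levels of TGF-β1 and exosomal PD-L1 without fixing a day.

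The samples feed two analyses. Section 6.2 lists among the secondary outcomes "Pre-treatment, serial post-treatment plasma EBV-DNA levels, and dynamics of" EBV DNA. Section 7.1 derives by ROC analysis "The cut-off values of baseline and changes in the exo-PD-L1" and TGF-β1 levels.

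**The concern.** A change from baseline is easiest to interpret when the baseline is taken just before the first dose, so that the whole interval is time on drug. Footnote m allows the baseline to be taken up to four weeks earlier, at a distance set by screening logistics and different for each patient. The recorded change then mixes time off drug with time on drug in varying proportions. The baseline level, for which section 7.1 also seeks a cut-off, is likewise taken at different distances from treatment.

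Part of the gap may fall under earlier treatment. Exclusion criterion 6 bars prior chemotherapy, targeted therapy or radiotherapy only within 2 weeks of Day 1, so a sample from Day -28 to -15 could be drawn while that therapy is still being given.

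At stake are EBV DNA dynamics, a secondary outcome, and the cut-offs for two exploratory markers in a cohort planned at 38 patients. A pre-dose sample that was never drawn cannot be recovered at analysis.

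**Working it through.** The plan states no figure to reproduce. The check is a reading of the footnotes followed by timing arithmetic.

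**Does any text restore the Day 1 sample?** Footnote i and section 6.1 are met for EBV DNA by any pre-treatment sample, including one at screening. For the other two markers they give only a frequency. Section 6.5 asks for pre-treatment levels, which a screening sample also satisfies, and for blood every 2 weeks over 8 weeks, with no pre-dose draw specified. The protocol can tighten a single row: footnote j requires the pregnancy test within 1 week before treatment. Nothing comparable covers the markers. The screening window is itself 28 days, so the time limit in footnote m excludes almost no screening sample.

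**Inputs.** Gap g between baseline sample and first dose: 0 to 28 days (screening window and footnote m). Days on drug d at the next sample: 14 for Cycle 2 Day 1, 56 for the 8-week TGF-β1 sample.

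**Formulas.** Interval = g + d. Off-drug share = g / (g + d).

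| Gap g (days) | Interval to Cycle 2 Day 1 | Off-drug share | Interval to week 8 | Off-drug share |
|---|---|---|---|---|
| 0 | 14 | 0% | 56 | 0% |
| 7 | 21 | 7/21 = 33% | 63 | 7/63 = 11% |
| 14 | 28 | 14/28 = 50% | 70 | 14/70 = 20% |
| 28 | 42 | 28/42 = 67% | 84 | 28/84 = 33% |

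**Visit windows.** Section 5.3 allows 3 days either side of the scheduled dose; the appendix gives 7 days on the cycle. The two need reconciling in any case. At g = 28, the share at Cycle 2 Day 1 runs from 28/45 = 62% to 28/39 = 72% under the 3-day window, and from 28/49 = 57% to 28/35 = 80% under the 7-day window.

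**Possible effect on a recorded change (assumptions only).** Suppose a marker doubles every T days off drug and truly falls by 50% in the first 14 days on drug. The recorded ratio is 0.5 × 2^(g/T). The documents give neither T nor the fall.

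| T (days) | g = 7 | g = 14 | g = 28 |
|---|---|---|---|
| 14 | -29% | 0% | +100% |
| 30 | -41% | -31% | -5% |
| 60 | -46% | -41% | -31% |
| 90 | -47% | -44% | -38% |

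In this model a 50% fall is recorded as a rise only when the gap exceeds the doubling time. The result runs from near-harmless to severe, depending on inputs that the documents do not supply.

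**The case against.** Footnote m permits and does not require. It applies only while the patient's condition is unchanged, and any patient with a Day 1 draw is unaffected. The biomarker row also has its own footnote, and on a specific-over-general reading the marker schedule follows footnote i and the grid. Baseline definitions and analysis windows are commonly left to a statistical analysis plan, which may exist.

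Most of this stands as a limit on the point. It does not remove it. The condition is clinical and undefined, and does not show that a circulating marker is stable. Footnote i does not contradict footnote m, because a screening sample meets its wording. An analysis plan can define a baseline but cannot supply a sample that was not drawn. A later sample is no substitute: the Background reports that in the first-in-human trial, above 1 mg/kg, the drug saturated peripheral PD-L1 and sequestered plasma TGF-β throughout dosing. The grid columns do not line up perfectly in the available copy, but the point rests on the footnote wording.

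A reader might infer more than the documents support:

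- That every patient's baseline is the screening sample. The waiver is optional, and how often it is used is unknown.
- That the protocol treats the interval as common to all patients. Sections 6.2 and 7.1 speak only of dynamics, baseline and changes, and define no interval.
- That the objectives are framed as change. Secondary objective 6 names the EBV DNA level, and exploratory objectives 2 and 3 name TGF-β1 and the exosomal PD-L1 profile. Change enters through sections 6.2 and 7.1, and the ROC change cut-off does not cover EBV DNA.
- That early changes will be reversed in sign. This depends wholly on assumed drift, and tumour-like doubling has no support in the documents for TGF-β1.

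**Conclusion.** The point holds as a minor weakness in a collection rule. Footnote m leaves the biomarker row open to a baseline 0 to 28 days before the first dose, possibly overlapping prior therapy, and nothing else in the protocol closes that gap. Where the waiver is used, up to 67% of a nominal 14-day change and up to 33% of a 56-day change is time off drug, before visit windows. These figures come from the schedule alone. The resulting bias or noise in the markers cannot be sized from the documents.

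The reach is EBV DNA dynamics (secondary) and the baseline and change cut-offs for exosomal PD-L1 and TGF-β1 (exploratory). The primary objective response rate, its two-stage rule and its sample size are untouched.

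**What to change.** In footnote m, exempt the exploratory blood-based biomarker row. In footnote i, state that the pre-dose sample on Cycle 1 Day 1 is to be drawn and is the baseline for EBV DNA, TGF-β1 and exosomal PD-L1. Keep the screening sample only as a fallback if the Day 1 sample is lost, with its collection date recorded so that the gap is known.

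This sets g to 0 and the off-drug share to 0% for every patient with a Day 1 sample. The interval to the next sample still varies with the visit window. The cost is two footnote edits and one blood draw, already marked in the grid, at a visit the patient attends for the infusion.
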